#### **Visit 8: Final visit at the end of 6 weeks**

Attend clinical research unit

Remove CGM, upload data to Medtronic Carelink iPro software, enter calibration data.

Switch off ABC4D and return device

Acceptability questionnaire to be completed.

[figure not shown]
Usual care will be maintained for diabetes throughout the study. No concomitant medical therapies are contra-indicated, except GLP-1 analogues and gliptins. Support will be offered to any participants who have concerns about their diabetes management.

Subjects using the ABC4D will have the opportunity to call a physician for medical support and an engineer for technical support 24 hours a day throughout the study.

**Statistics** 20 subjects planned to be enrolled. This is not a randomised study and there are no comparison or control groups. Outcomes from the study are absolutes as described above. The sample size is comparable to other technology transfer studies, is a realistic number for recruitment and provides robust clinical validation and safety data. The study is not powered to show a change in the primary or secondary outcomes compared with usual care but is an assessment of a new technology.

Missing, unused, and spurious data will be assessed on an individual basis and may be ignored, withdrawn or the visit may be removed from the analysis with appropriate justification adjudicated by the Principal Investigator.

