## Phase 2 of ABC4D study: Summary of visits

## Phase 3

**Objective:** To demonstrate efficacy of the ABC4D

**Methodology** Randomised open-label study

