**Secondary outcomes:**

HbA1c at 3 months  
Post-prandial AUC at 4 hours and 6 hours  
Post-prandial AUC (<3.9) at 4 hours and 6 hours  
Episodes of hypoglycaemia within 4- and 6-hours post-prandially  
% time in target glucose (3.9-10mmol/l)  
% time in hypo- (<3.9mmol/l) and hyperglycaemia (>10mmol/l)  
Glycaemic risk: LBGI and HBGI  
Glycaemic variability: MAGE and CONGA-2  
Change in weight (kg)  
Number achieving target HbA1c (≤ 53 mmol/mol)  
24-hours insulin dose requirements  
PAID score questionnaire  
DQOL questionnaire  
DTSQ Questionnaire  
Acceptability questionnaire (non-validated)

These are validated, published metrics.

**Timescale:** Each subject will be in the study for 6 months. It is anticipated that it will take 15 months to complete the 4th phase.

**Population:** 142 subjects with T1DM, are required to demonstrate an HbA1c difference of 0.6% with  $\alpha$  of 0.05 and 90% power (two-tailed). We aim to screen n=180 and randomise n=90 in each group. This power calculation is based on using a population mean HbA1c of 7.9% with a standard deviation of 1.1.

The first 25 participants will be randomised to either the ABC4D running in semi-automatic mode (where the revisions are done using a semi-automatic process-see page 23) or a standard bolus calculator. The remaining participants will be randomised to either the fully automated ABC4D (where revisions are fully automated) or a standard bolus calculator. Screening 180 participants will ensure that at least 142 participants are included to enable demonstration of a significant difference between the fully automated ABC4D system and a standard bolus calculator.

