### Visit 2: CGM review and control study start

- Attend 4 weeks after visit 1
- Remove CGM, upload data to DiaSend/Dexcom Studio software (subject can do upload the data at home prior to attending the visit) and review data with subject.
- Adjust ICR, ISF and basal rates if deemed necessary based on CGM data.

Follow-up clinic visits at 1 month, 3 months and 6 months:

### Visit 3

Review at 1 month:

- Review of subject's diabetes control including insulin requirements, incidence of hypoglycaemia, exercise, driving etc.

### Visit 4

Review at 3 months:

- Review of subject's diabetes control including insulin requirements, incidence of hypoglycaemia, exercise, driving etc.
- Random venous blood taken for HbA1c
- Weight (kg)

### Visit 5

Review at 6 months:

- Review of subject's diabetes control including insulin requirements, incidence of hypoglycaemia, exercise, driving etc.
- Random venous blood taken for HbA1c
- Weight (kg)
- PAID score questionnaire and acceptability questionnaire to be completed

Usual care will be maintained for diabetes throughout the study. No concomitant medical therapies are contra-indicated, except GLP-1 analogues, SLGT2 inhibitors and gliptins. Support will be offered to any participants who have concerns about their diabetes management.

Subjects in the intervention group using the ABC4D will have the opportunity to call a physician for medical support and an engineer for technical support 24 hours a day throughout the study.

*Statistics* This is a randomised study with an intervention group and a control group. Outcomes from the study are absolutes as described above. 142 subjects with T1DM, are required to demonstrate an HbA1c difference of 0.6% with  $\alpha$  of 0.05 and 90% power (two-tailed). We aim to screen n=160 and randomise n=80 in each group. This power calculation is based on using a population mean HbA1c of 7.9% with a standard deviation of 1.1.

The sample size is comparable to other technology transfer studies, is a realistic number for recruitment and provides robust clinical validation and safety date of a new technology.

[figure not shown]
Missing, unused, and spurious data will be assessed on an individual basis and may be ignored, withdrawn or the visit may be removed from the analysis with appropriate justification adjudicated by the Principal Investigator.

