Research participants will benefit from being in the study by having increased access to diabetes professionals and more frequent visits to hospital with an emphasis on improved glycaemic control. They will also have the opportunity to use continuous glucose monitoring and review the results with a diabetologist experienced with monitoring. The benefits to people with T1DM include the potential to carry forward technology to improve the risks of high glucose concentration leading to complications and distressing low glucose values.

**Data** During the course of the study visits some data will be stored on laptop computers, not connected to the Internet, for later statistical analysis. These data will be coded and non identifiable. Participant data will be stored in a locked filing cabinet in a secure room in Imperial College Healthcare NHS Trust. Only the research team will have access to the filing cabinet.

Electronic data will be stored by subject number only on NHS desktop computers which are in the same locked room. Only the research fellow and nurse will have access to the data.

Laptop computers may be used during the visits for portability and convenience. At the end of each visit the anonymised data will be transferred immediately to the secure NHS computers and will be deleted from the laptop. Access to NHS computers is only by members of NHS staff with appropriate login privileges.

All data will be stored in an anonymised form by using study numbers for identification of participants. The NHS code of confidentiality will be followed and all activity will meet the requirements of the data protection act.

Only members of the clinical research team and those responsible for direct care will have access to subjects' data during the study. The data generated by the study will be analysed by the research team including the engineering team from Imperial College. The analysis will be on anonymised data and will take place in Imperial College Healthcare NHS Trust and in Imperial College academic buildings, both in the Faculty of Medicine and in the Faculty of Engineering.

**Fully anonymised glucose, insulin and carbohydrate data, along with the ABC4D parameters (including time, day, exercise, alcohol, menstrual cycle) may be shared with collaborators including Dexcom to support further development**

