For phase 3 and 4 of the study a data monitoring committee will be convened to assess the data collected throughout the study. This committee will comprise of the PI ([name]), [name], [name], a lay member, an independent diabetologist and an independent scientist and will meet twice a month.

**Safety** During intercurrent illness, subject visits will be postponed as insulin requirements will be altered. Adverse events will be reported to the REC, the sponsor and the Principal Investigator immediately. Full reports will be submitted through the Imperial College Healthcare Datix system. Subjects will be followed-up after one week following an adverse event and thereafter in the diabetes clinic or any other clinically indicated follow up.

**Direct Access to Source Data/Documents** The investigator(s)/institution(s) will permit trial-related monitoring, audits, IRB/IEC review, and regulatory inspection(s), providing direct access to source data/documents.

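### Randomised Phases 3 and 4 reuse the uncontrolled phases' data rule: the PI may drop data or visits case by case, on a justification with no set criteria and no masking to arm

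*Combined protocol and SAP*

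**What the plan says.** The Statistics paragraphs of all four phases contain the same data-handling sentence. It begins "Missing, unused, and spurious data will be assessed on an individual basis and may be ignored, withdrawn or the visit may be removed". Read to its end, it says that such data "may be ignored, withdrawn or the visit may be removed from the analysis with appropriate justification adjudicated by the Principal Investigator".

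In Phases 1 and 2 it sits beside the statement "This is not a randomised study and there are no comparison or control groups". Phase 3 is a "Randomised open-label study", Phase 4 Methodology uses the same words, and the primary outcome of both is HbA1c at 6 months, from a venous sample at the 6-month review.

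Other text bears on the point:
- **Data:** "The analysis will be on anonymised data". The analysis is done by the research team, including the engineers.
- **Data monitoring committee (Phases 3 and 4):** "This committee will comprise of the PI", two further named members, a lay member and two independent members. No role in exclusions is stated.
- **Study Management:** there are monthly data reviews, and a management team that includes an uninvolved diabetologist. Again no role in exclusions is stated.
- **Consent:** participants whom the clinician moves to alternative treatment stay in follow-up and in the analysis.
- **Subject withdrawal criteria (Phases 3 and 4):** withdrawal is immediate, with follow-up in routine clinic. Later study HbA1c is not mentioned.

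**The concern.** With no comparison group, case-by-case removal cannot distort a difference between arms. In Phases 3 and 4 it can. The sentence asks for a justification but does not say what counts as one, and it does not define unused or spurious data. Removing the 6-month visit removes the primary outcome, and ignoring missing values amounts to a complete-case analysis.

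If such decisions depend on arm and outcome, even unintentionally, the HbA1c difference is biased and the type I error exceeds its nominal level. No as-randomised analysis is specified against which a reader could check the result. Because the analysed population is not fixed in advance, the true error rate cannot be stated. Ordinary dropout also triggers the rule, with no selective intent.

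The CGM-derived secondary outcomes are probably more exposed than HbA1c, since unused and spurious describe sensor and app data more naturally than a single laboratory result.

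**Working it through.** **1. The plan's own figure.** Inputs from Statistics, Phases 3 and 4: difference 0.6, SD 1.1, two-sided alpha 0.05, power 90%.

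n per arm = 2 × SD² × (z₀.₉₇₅ + z₀.₉₀)² / difference² = 2 × 1.21 × (1.960 + 1.282)² / 0.36 = 70.6, so 71 per arm and 142 in total. The stated 142 reproduces.

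**2. Arm sizes.** Phase 3, and Statistics in Phase 4, give 80 per arm ("We aim to screen n=160 and randomise n=80 in each group"). Phase 4, Population gives 90 ("We aim to screen n=180 and randomise n=90 in each group"). That conflict is a separate matter, so both sizes are used in step 3.

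**3. Dropping the k highest values from one arm.** The values of k are assumed, and there is no true effect. Expected shift = −(sum of the k largest expected deviations from the mean) / (n − k). For n = 80 and SD 1.1, the five largest expected deviations are 2.67, 2.26, 2.03, 1.87 and 1.74 points. For k = 2: −(2.67 + 2.26)/78 = −0.063. For k = 5: −10.57/75 = −0.141. Type I error comes from 40,000 simulated trials per cell (two-sample t-test, two-sided 5%).

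| k dropped | n = 80: shift, error | n = 90: shift, error |
|---|---|---|
| 1 | −0.034, 5.8% | −0.031, 5.8% |
| 2 | −0.063, 7.1% | −0.057, 7.1% |
| 4 | −0.116, 11.4% | −0.105, 11.0% |
| 5 | −0.141, 14.3% | −0.128, 13.4% |

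Removal unrelated to value gives no shift and an error of about 5%. Taking 4-5 values at random from the top fifth of one arm gives −0.07 to −0.10 and 7-9%. Dropping the 4-5 highest from both arms gives no shift and 7-8%.

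**4. Missing values ignored.** Assume the margin 160 − 142 = 18 is an allowance for loss, so 9 of 80 per arm. Assume intervention losses fall at random in the upper half of 3-month HbA1c and control losses fall at random. Assume correlations of 0.5, 0.7 or 0.85 between visits.

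The upper half lies on average 1.1 × 0.798 = 0.878 above the mean. The complete-case shift is therefore about −(9/71) × 0.878 × correlation = −0.056, −0.078 or −0.095. Simulation (8,000 trials each) gives −0.055, −0.075 and −0.094, with errors of 6.3%, 6.6% and 7.6%.

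A likelihood estimate using baseline and 3-month values gives 0.00 and about 5%. That holds because loss depends here only on an observed value. If loss instead falls in the upper half of 6-month HbA1c, the same estimate keeps a bias of about −0.07, −0.05 and −0.03 at the three correlations.

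The margin is itself uncertain. Phase 4, Population sets the first 25 participants apart, leaving 180 − 25 = 155 and a margin of 13, or about 6 per arm; (6/71) × 0.878 × correlation gives −0.04 to −0.06. If all 180 − 142 = 38 were losses (19 per arm), (19/71) × 0.878 × correlation gives about −0.12 to −0.20.

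**5. CGM weeks in Phase 3.** The intervention arm has 4 weekly uploads (days 7 to 28) plus 5 (weeks 8, 12, 16, 20, 24), so 9. Control has 3 (weeks 4, 12, 24). If all weeks are used, removing one upload costs 1/9 of a participant's data in one arm and 1/3 in the other.

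**The case against.** The strongest reply is that the rule is not unconditional. It requires a justification, names no outcome, and in ordinary use would clean sensor data. Consent keeps some participants in the analysis, data are anonymised, and several oversight bodies exist. The larger figures need someone to remove only the highest values from only one arm and to justify each removal, which is misuse of the rule.

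Much of this stands. That HbA1c falls under the rule, and that the PI knows the arm, are inferences from unrestricted wording, an open-label design and the absence of any masking provision. The documents state neither. A reader might infer that the investigators plan selective exclusion, or that 11-14% is this trial's error rate; nothing supports either reading. A reader might also see a contradiction between Consent and the withdrawal criteria. It is an ambiguity: Consent may or may not reach withdrawn participants. The 9 against 3 CGM weeks show unequal data volume in Phase 3, not bias, and do not carry over to Phase 4, where both arms use real-time CGM throughout.

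What does not stand is that these safeguards close the gap. Anonymised is not masked to arm, no oversight body is given a part in exclusions, and the Consent sentence does not address removed visits or missing results.

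A further objection concerns the remedy. Simply requiring all randomised participants would, in Phase 4, pool two device versions, because the first 25 are randomised with the semi-automatic mode and the 142 are meant for the fully automated comparison. That objection is correct, and the fix allows for it.

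**Conclusion.** The concern holds as a defect in a stated rule. In two randomised, open-label phases, the rule lets the analysed population depend on arm and outcome, without criteria or masking, and with only a partial as-randomised safeguard. It permits such exclusions and does not prescribe them.

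The size is unknown because the rule has no criteria. Under the assumed scenarios (normal values, SD 1.1, no true effect, 80 per arm), one or two selective removals have a small effect. The deliberate worst case of 4-5 moves the difference by 19-23% of the 0.6 target (0.116/0.6 to 0.141/0.6). Ignoring nine outcome-related losses per arm falls between these. The removal counts, loss pattern and correlations are not in the documents. No bias was calculated for the CGM outcomes.

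Confidence is high in the gap itself. The magnitudes are illustration only. The sentence should be replaced before any results by arm are seen, because afterwards legitimate cleaning cannot be told apart from post hoc exclusion.

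**What to change.** For Phases 3 and 4, replace the sentence with the following.

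- **(a) Analysis set.** The primary analysis includes, in the arm assigned, everyone randomised to the comparison it addresses. In Phase 4, first reconcile this with Population and with the section on case base revision. State whether the primary comparison is all randomised participants, or those randomised after the first 25 (fully automated ABC4D against standard calculator, with concurrent controls). The other becomes a sensitivity analysis.
- **(b) HbA1c exclusions.** Exclude a result only for a documented laboratory or sample failure, judged by an existing team member masked to arm before results by arm are seen. List exclusions by arm.
- **(c) Missing 6-month HbA1c.** Use one pre-stated method drawing on baseline and 3-month values, for example a mixed model, plus a missing-not-at-random sensitivity analysis. The second part is needed because step 4 shows that the model alone does not remove bias when loss depends on the unobserved value.
- **(d) Withdrawal.** Reconcile the withdrawal criteria with Consent. Still collect 3- and 6-month HbA1c after device discontinuation or withdrawal where consent and circumstances allow.
- **(e) CGM and app data.** Write one exclusion rule and apply it identically in both arms. In Phase 3, apply it at the shared weeks 4, 12 and 24.

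Cost: protocol and SAP wording, a few extra HbA1c samples and a little more analysis. Sample size, and visits for those who stay on study, do not change.

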**Table: Overview of activities at each visit for subjects in the intervention group**

Activity / Visit no	1	2	3	4	5	Additional information
Insertion of CGM sensor	x					Subjects will change the sensor every week at home throughout the study (24 weeks)
Removal of CGM sensor					x	
Food diary	x					
CGM review with subject		x				
Initialise CBR algorithm and ABC4D start		x				
Update CBR algorithm with new cases					x	This will be done automatically with remote supervision every 1 week throughout the study

Clinical examination	X					
Weight measurement	X			X	X	
Venous blood test	X			X	X	
Urine test	X					
Pregnancy test	X					
ECG	X					
Questionnaire/s	X					
Follow-up clinical review		X	X	X	X	

## Phase 4 of ABC4D study: Overview of study

**The following information applies to all four phases of the study:**

***Potential risks and benefits***

The potential risks and burdens for research participants are as follows:

At the beginning of each phase of the study there is a venous blood test and in addition the 1st phase includes insertion of an intravenous cannula. These have the potential to cause discomfort. This will be minimised by experienced research personnel and appropriate use of equipment.

During the studies, subjects will have a subcutaneous CGM sensor inserted. Sensor insertion can be associated with some discomfort but the insertion devices are spring-loaded with introducers, making the process rapid and often painless. Any discomfort will be minimised by adhering to manufacturer's instructions.

During the time subjects are using the ABC4D there is a risk from the new technology. The ABC4D may suggest an insulin dose too high or too low potentially resulting in hypo- or hyperglycaemia. In the Phase 1 study subjects are closely monitored in a controlled supervised environment to ensure safety of the ABC4D. In addition, subjects will be given contact phone numbers to call a physician for medical support and an engineer for technical support 24 hours a day throughout phase 2 and 3 of the study.

Insulin will be administered subcutaneously by the subject as per their usual basal-bolus insulin regime. The subcutaneous route is the standard route of insulin administration in T1DM irrespective of whether they are on MDI or pump therapy.

It is acknowledged that the clinical schedule is demanding of subject's time and includes frequent visits to the clinical research unit. This inconvenience is necessary to adequately and safely validate the device. We will minimise the burden as much as possible by making every effort to schedule visits around subject's lifestyles, and by being flexible with attendances at the St Mary's, Charing Cross or Hammersmith campuses of Imperial College Healthcare NHS Trust.

Research participants will benefit from being in the study by having increased access to diabetes professionals and more frequent visits to hospital with an emphasis on improved glycaemic control. They will also have the opportunity to use continuous glucose monitoring and review the results with a diabetologist experienced with monitoring. The benefits to people with T1DM include the potential to carry forward technology to improve the risks of high glucose concentration leading to complications and distressing low glucose values.

**Data** During the course of the study visits some data will be stored on laptop computers, not connected to the Internet, for later statistical analysis. These data will be coded and non identifiable. Participant data will be stored in a locked filing cabinet in a secure room in Imperial College Healthcare NHS Trust. Only the research team will have access to the filing cabinet.

Electronic data will be stored by subject number only on NHS desktop computers which are in the same locked room. Only the research fellow and nurse will have access to the data.

Laptop computers may be used during the visits for portability and convenience. At the end of each visit the anonymised data will be transferred immediately to the secure NHS computers and will be deleted from the laptop. Access to NHS computers is only by members of NHS staff with appropriate login privileges.

All data will be stored in an anonymised form by using study numbers for identification of participants. The NHS code of confidentiality will be followed and all activity will meet the requirements of the data protection act.

Only members of the clinical research team and those responsible for direct care will have access to subjects' data during the study. The data generated by the study will be analysed by the research team including the engineering team from Imperial College. The analysis will be on anonymised data and will take place in Imperial College Healthcare NHS Trust and in Imperial College academic buildings, both in the Faculty of Medicine and in the Faculty of Engineering.

**Fully anonymised glucose, insulin and carbohydrate data, along with the ABC4D parameters (including time, day, exercise, alcohol, menstrual cycle) may be shared with collaborators including Dexcom to support further development**

For phase 3 and 4 of the study a data monitoring committee will be convened to assess the data collected throughout the study. This committee will comprise of the PI ([name]), [name], [name], a lay member, an independent diabetologist and an independent scientist and will meet twice a month.

**Safety** During intercurrent illness, subject visits will be postponed as insulin requirements will be altered. Adverse events will be reported to the REC, the sponsor and the Principal Investigator immediately. Full reports will be submitted through the Imperial College Healthcare Datix system. Subjects will be followed-up after one week following an adverse event and thereafter in the diabetes clinic or any other clinically indicated follow up.

**Direct Access to Source Data/Documents** The investigator(s)/institution(s) will permit trial-related monitoring, audits, IRB/IEC review, and regulatory inspection(s), providing direct access to source data/documents.

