### **Clinical review at 1 month, 3 months and 6 months:**

*Review at 1 month (coincides with visit 4):*

- Review of subject's diabetes control including insulin requirements, incidence of hypoglycaemia, exercise, driving etc.

*Review at 3 months (coincides with visit 6):*

- Review of subject's diabetes control including insulin requirements, incidence of hypoglycaemia, exercise, driving etc.
- Random venous blood taken for HbA1c
- Weight (kg)

*Review at 6 months (coincides with visit 8):*

- Review of subject's diabetes control including insulin requirements, incidence of hypoglycaemia, exercise, driving etc.
- Random venous blood taken for HbA1c
- Weight (kg)
- PAID score, DQOL and DTSQ questionnaires to be completed

Usual care will be maintained for diabetes throughout the study. No concomitant medical therapies are contra-indicated, except GLP-1 analogues, SGLT2 inhibitors and gliptins. Support will be offered to any participants who have concerns about their diabetes management.

Subjects in the intervention group using the ABC4D will have the opportunity to call a physician for medical support and an engineer for technical support 24 hours a day throughout the study.

**Statistics** This is a randomised study with an intervention group and a control group. Outcomes from the study are absolutes as described above. 142 subjects with T1DM, are required to demonstrate an HbA1c difference of 0.6% with  $\alpha$  of 0.05 and 90% power (two-tailed). We aim to screen n=160 and randomise n=80 in each group. This power calculation is based on using a population mean HbA1c of 7.9% with a standard deviation of 1.1.

The sample size is comparable to other technology transfer studies, is a realistic number for recruitment and provides robust clinical validation and safety date of a new technology.

[figure not shown]
Missing, unused, and spurious data will be assessed on an individual basis and may be ignored, withdrawn or the visit may be removed from the analysis with appropriate justification adjudicated by the Principal Investigator.

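### In the open-label phases 3 and 4, the Principal Investigator decides case by case, without criteria or masking, which data leave the analysis, and also sits on the committee that assesses the accumulating data

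*Combined protocol and SAP*

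**What the plan says.** **The committee.** The Data paragraph in the part that applies to all four phases says: "For phase 3 and 4 of the study a data monitoring committee will be convened to assess the data collected throughout the study". On membership it says "This committee will comprise of the PI", then lists two further people whose names are removed from the public text, and then "a lay member, an independent diabetologist and an independent scientist and will meet twice a month".

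**Exclusions.** The Phase 3 Statistics paragraph says that missing, unused and spurious data are looked at individually and "may be ignored, withdrawn or the visit may be removed from the analysis with appropriate justification adjudicated by the Principal Investigator". The Phase 4 Statistics paragraph repeats the rule, ending "the visit may be removed from the analysis with appropriate justification adjudicated by the Principal Investigator".

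**Blinding.** The Methodology line of Phase 3 reads "Randomised open-label study", and Phase 4 uses the same words. In both phases the primary outcome is HbA1c at 6 months.

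**Other access to data.** Study Management provides for weekly research meetings and monthly data reviews, chaired by the chief investigator or another senior researcher. Under Data, the research team, including the engineers, analyses the data.

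**Not stated anywhere.** There is no committee charter, no split into open and closed sessions, no rule on whether summaries are pooled or by arm, no interim analysis plan, no definition of spurious data, and no requirement that exclusions be decided without knowledge of arm or result.

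**The concern.** Two roles meet in one person. The first is open-ended discretion over which observations count in a randomised comparison. The second is a seat on the body that assesses those observations as they accumulate. Either role calls for a safeguard; together, and with allocation unmasked, they call for one more strongly.

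At stake is the credibility of the primary HbA1c comparison. An HbA1c value or visit judged spurious by someone who knows the arm, and perhaps the direction of the results so far, cannot later be shown to have been judged neutrally. No bad faith is needed: unusual values that contradict an expected benefit tend to attract more scrutiny than those that support it.

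**Working it through.** **1. The plan's own figure.** The Statistics paragraphs of phases 3 and 4 give a difference of 0.6, SD 1.1, two-sided alpha 0.05 and power 90%.

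n per arm = 2 × [(1.960 + 1.282) × 1.1 / 0.6]² = 70.6, so 71 per arm and 142 in total.

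This matches the stated 142. The sample size is not in question.

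**2. Do the two roles overlap in time?** Each randomised phase is expected to last 15 months (for Phase 4, "It is anticipated that it will take 15 months to complete the 4th phase"). Two meetings a month give 2 × 15 = about 30 meetings per phase. If the 15 months run from first enrolment, no 6-month HbA1c exists before about month 6 in Phase 3, or about month 7 in Phase 4 because of its 4-week run-in.

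- Phase 3: (15 − 6) × 2 = about 18 meetings at which some primary data could exist.
- Phase 4: (15 − 7) × 2 = about 16 such meetings.

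The 3-month HbA1c, a secondary outcome, would be available earlier. So committee work and accrual of primary data overlap for a substantial part of each phase.

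**3. What limits the discretion?** Setting the passages side by side:

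- Who decides: the Principal Investigator, in both phases.
- On what criteria: an appropriate justification, not further defined.
- Knowing what: allocation is open; what the committee is shown is not specified.
- When: no deadline relative to database lock or to any by-arm summary.

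**4. How sensitive is the result to a few decisions?** This is an illustration, not a prediction. Assume no true effect, normal HbA1c with SD 1.1, 80 per arm (the number in the Phase 4 Statistics paragraph), and removal of the k highest values from the intervention arm only.

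Shift = k × (mean of the removed values above the arm mean) / (80 − k)

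- k = 2: the top two of 80 average about 2.24 SD, or 2.24 × 1.1 = 2.46. Shift = 2 × 2.46 / 78 = 0.06. Simulated two-sided type I error is about 7%.
- k = 4: the top four average about 2.01 SD, or 2.01 × 1.1 = 2.21. Shift = 4 × 2.21 / 76 = 0.12, which is 0.12 / 0.6 = one fifth of the target difference. Simulated type I error is about 11%.

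The simulation used 100,000 null trials and a two-sample t-test at 5%. With no removals it rejected 5.0%.

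**The case against.** **By-arm review is not stated.** A reader might infer that the Principal Investigator will see comparative results twice a month. The text says only that the committee assesses the data collected. Silence is not a plan to unblind, so this objection stands. What remains is that no restriction is written.

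**Repeated looks do not inflate type I error here.** A reader might also infer that some 30 meetings amount to 30 interim tests. No interim test, boundary or early-success rule is planned. Looking without acting on a test leaves the final analysis at 5%, and most early meetings would have no 6-month HbA1c to compare. This stands in full, and no error rate for repeated looks should be attached to the plan.

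**The committee has independent members.** It does: an independent diabetologist, an independent scientist and a lay member. The management team, which reviews data between phases, also includes a consultant diabetologist not involved with the study. None of them is given the decision on exclusions.

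**HbA1c is a laboratory measure.** That protects the measurement, not the choice of which visits are analysed. The Consent paragraph keeps participants given alternative treatment in the data analysis, which closes one route to exclusion, but it does not govern data judged spurious.

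**Removing the Principal Investigator from by-arm data would not close every route.** This is partly right. The monthly data reviews would have to be covered too, and an open-label team will still know individual allocations. The absence of exclusion criteria would also be a weakness if the Principal Investigator left the committee.

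**The two roles might belong to different people.** Reading PI and Principal Investigator as the same role is natural. The protocol also uses Chief Investigator without saying how the roles relate.

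**Conclusion.** The point holds as a gap in safeguards; the label is cheap improvement. As written, the rule allows an unmasked person who sits on the committee assessing accumulating data to choose, without criteria, what enters the primary comparison in both randomised phases.

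The documents do not show that by-arm results are reviewed, that efficacy is tested before the end, or that any exclusion was made improperly. The actual bias cannot be quantified from them. The shifts of 0.06 and 0.12 percentage points show only that two to four one-sided decisions among 80 would matter. They rest on no true effect, normality, the protocol's SD, and removal of the most extreme values in one arm.

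**What to change.** 1. **Phase 3 and Phase 4 Statistics paragraphs.** Replace adjudication by the Principal Investigator with decisions by the independent diabetologist and the independent scientist already on the committee. They work from listings by study number with arm removed. All decisions are completed and logged, with reasons, before any by-arm summary is produced. Add a sensitivity analysis that keeps every recorded HbA1c value. In Phase 3 the CGM schedules differ between arms, so CGM listings should be limited to the weeks both arms share (4, 12 and 24); otherwise the schedule reveals the arm.

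2. **Data paragraph, on the committee.** Have the Principal Investigator attend only for pooled conduct data. Confine any by-arm summaries to the independent and lay members; whether the two members whose names are removed qualify depends on their independence, which the public text does not show. State that no between-arm efficacy comparison is made before the final analysis.

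3. **Study Management.** Apply the same pooled-only limit to the monthly data reviews.

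**Cost.** Protocol or charter wording and some time from two existing members; no new members, visits or participants. The Principal Investigator gives up sole control of exclusions and does not see by-arm summaries during the trial. Individual allocations remain known to the team, so the change reduces the exposure without removing it.
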